8.5 ECG

A 12-lead ECG will be obtained at the initial screening visit and at the Day 14 visit. The 12-lead ECGs will be performed with the subject in the recumbent position after 5 minutes of rest.

8.6 Hematology, Serum Chemistry, and Urinalysis

Blood and urine for clinical safety laboratory assessments will be collected at the initial screening visit, Day 0 (serum chemistry only), and on Day 14. The samples will be prepared using standard procedures. A detailed listing of the hematology, serum chemistry, and urinalysis tests that will be

performed is provided in Appendix B. A regional laboratory will perform the clinical laboratory tests.

In addition, at Day 7, blood will be collected for a subset of serum chemistry tests. Specifically, the testing will be limited to creatinine (and calculation of creatinine clearance) and electrolytes (sodium, bicarbonate, calcium, chloride, phosphorous, and potassium).

Also, if the subject's BP at Day 7 is too elevated for them to continue safely in the study (i.e., $SBP_{24h} > 169$ mmHg and/or $DBP_{24h} > 110$ mmHg), blood will be drawn for renal profile testing (non-fasting). The renal profile testing will include the following tests: creatinine, calcium, chloride, carbon dioxide, albumin, blood urea nitrogen (BUN), protein, phosphorus, glucose, and potassium.

9. ASSESSMENT OF PHARMACOKINETICS

9.1 Blood Collection

Subjects will have a venous blood sample collected at 24 hours \pm 1 hour post-dose on Day 14 to measure plasma concentrations of amlodipine. Only subjects enrolled at Investigational Sites that have UV-shielded lights will participate in the PK blood collection. Due to the design of the trial (randomized, double-blind, placebo-controlled), this blood sample will be collected and analyzed for all participating subjects, regardless of whether they are in a treatment arm that receives amlodipine.

See PK procedures manual for specific information regarding the procedures for PK blood sample collection, processing, and shipment to bioanalytical laboratory.

9.2 Bioanalytical Method

Plasma samples will be assayed for amlodipine by a Sponsor designated laboratory using a validated LC-MS/MS method.

9.3 Pharmacokinetic Analysis

As blood will only be collected at a single time point in this trial, plasma concentration-time curves and noncompartmental analyses are not planned. See Section 10 for planned statistical analysis of plasma concentration data.

10. STATISTICS

10.1 Data Sets

10.1.1 Intent-to-Treat (ITT)

The ITT data set will be comprised of randomized subjects with at least a valid baseline (Day –1 to Day 0) ABPM measurement and either

- a) A valid final (Day 13 to Day 14) ABPM measurement, where a subject completes the treatment program.

or

- b) A valid Day 6 to Day 7 ABPM measurement, where a subject is withdrawn from the treatment program at that point because of an $SBP_{24h} > 169$ mmHg and/or a $DBP_{24h} > 110$ mmHg, or if they are withdrawn for any other reason.

As noted in Section 6.4, if at the time of the Day 7 clinic visit subjects have too elevated a BP to be able to continue safely in the study (i.e., $SBP_{24h} > 169$ mmHg or $DBP_{24h} > 110$ mmHg), the study drug will be discontinued and the subjects will be instructed to resume taking their prescribed BP medication as directed by the study doctor or general practitioner. In this case, both mixed model for repeated measures (MMRM) and last observation carried forward (LOCF) techniques will be used with comparative sensitivity analysis.

Subjects that do not have the two paired valid ABPM measurements, as required (baseline and final, for those who complete the treatment program, or baseline and Day 6 to Day 7, for those withdrawn from the study), will not be included.

10.1.2 Per-protocol (PP)

The PP data set will be comprised of randomized subjects with at least a valid baseline (Day –1 to Day 0) ABPM measurement and also a valid final (Day 13 to Day 14) ABPM measurement.

Dropouts and subjects who had major violations of the protocol will be excluded. Major protocol violations will include missing more than 25% of scheduled doses of study drugs, and taking prohibited medications including any NSAIDs or calcium channel blockers (other than the study drugs).

All randomized subjects should receive their initial dose of study drugs in the clinic immediately following randomization.

10.2 Statistical Analysis of Efficacy Data

10.2.1 Primary Efficacy Endpoint

The primary efficacy endpoint for this trial will be the difference in the mean reduction in SBP_{day} from the baseline (Day –1 to Day 0) ABPM measurement to the final (Day 13 to Day 14) ABPM

measurement, where a subject completes the 14-day treatment plan, or to the Day 6 to Day 7 ABPM measurement, where a subject is withdrawn from treatment at Day 7, between subjects treated with amlodipine tablets (10 mg) and celecoxib capsules (200 mg) given together (arm 1) and amlodipine tablets (10 mg) given alone (i.e., with matched celecoxib placebo) (arm 2).

The primary efficacy endpoint will be that the lower limits of the 95% confidence interval for SBP_{day} reduction in treatment arm 1 will be at least 50% of the mean reduction in treatment arm 2.

10.2.2 BP Change Comparisons

Statistics are based on the reduction in BP from the baseline ABPM measurement (Day –1 to Day 0) to the post-dose ABPM measurement (Day 13 to Day 14 or if a LOCF is required Day 6 to Day 7), as this represents the efficacy of the treatment. Reductions will be, therefore, represented by positive numbers and increases by negative numbers. For this reason, the change in BP from baseline to final ABPM measurement will be a paired subtraction of the final ABPM measurement from the baseline ABPM measurement. Sensitivity analysis will compare these results with those of the PP dataset and an MMRM analysis.

10.2.3 Primary Efficacy Endpoint Analysis

A two-sample t-test will be used to test the one-sided hypothesis that treatment with amlodipine tablets (10 mg) and celecoxib capsules (200 mg) given together (arm 1) is non-inferior to half of the effect achieved with the control treatment with amlodipine tablets (10 mg) given alone (with matched celecoxib placebo) (arm 2).

$$H_0: \Delta SBP_{day,1} - 0.5(\Delta SBP_{day,2}) \geq 0 \text{ mmHg}$$

$$H_1: \Delta SBP_{day,1} - 0.5(\Delta SBP_{day,2}) < 0 \text{ mmHg}$$

Where $\Delta SBP_{day,1}$ is the change, for subjects in arm 1, in the SBP_{day} from the baseline ABPM measurement ($SBP_{day,1,0}$) to the final ABPM measurement ($SBP_{day,1,14}$).

$$\Delta SBP_{day,1} = SBP_{day,1,0} - SBP_{day,1,14}.$$

$\Delta SBP_{day,2}$ is the change, for subjects in arm 2, in SBP_{day} from the baseline ABPM measurement ($SBP_{day,2,0}$) to the final ABPM measurement ($SBP_{day,2,14}$).

$$\Delta SBP_{day,2} = SBP_{day,2,0} - SBP_{day,2,14}.$$

Refer to Appendix H for further details regarding the efficacy analysis, and in particular the non-inferiority margin.

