

Statistical Methods for Primary Efficacy Analysis:
	
The primary efficacy endpoint for this trial will be the difference in the mean reduction in SBP_{day} from Day 0 to Day 14 between subjects treated with amlodipine tablets (10 mg) and celecoxib capsules (200 mg) given together (arm 1) and amlodipine tablets (10 mg) given alone (with matched celecoxib placebo) (arm 2), and specifically that the lower limit of the 95% confidence interval for the arm 1 subjects is at least 50% of the mean reduction in the arm 2 subjects.
 
A two-sample t-test will be used to test the one-sided hypothesis that treatment with amlodipine tablets (10 mg) and celecoxib capsules (200 mg) given together (arm 1) is non-inferior to the control treatment with amlodipine tablets (10 mg) given alone (with matched celecoxib placebo) (arm 2).
 $H_0: \Delta SBP_{day,1} - 0.5(\Delta SBP_{day,2}) \geq 0$ $H_1: \Delta SBP_{day,1} - 0.5(\Delta SBP_{day,2}) < 0$ 
Where $\Delta SBP_{day,1}$ is the reduction in SBP_{day} for subjects in arm 1. $\Delta SBP_{day,2}$ is the reduction in SBP_{day} for subjects in arm 2.
 
For the primary analysis, an intent-to-treat (ITT) data set will be used comprising of randomized subjects with a valid ABPM measurement from Day -1 to Day 0 and also either a valid ABPM measurement from Day 13 to Day 14, where a subject completes the 14-day treatment plan, or a valid ABPM measurement from Day 6 to Day 7, where a subject is withdrawn from treatment at Day 7 because of an SBP_{24h} > 169 mmHg and/or a DBP_{24h} > 110 mmHg.

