### **1.3.7. Definition of change from baseline**

For all efficacy endpoints, the mean change will be computed considering the difference between the value at endpoint and the value at baseline (Endpoint minus Baseline). The protocol states the mean change as baseline minus endpoint. This change does not affect the absolute value of the results but gives a more intuitive interpretation of the direction of change (i.e., with a negative value indicating a decrease in BP over time and a positive value indicating an increase in BP over time).

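### The protocol's primary hypotheses run the wrong way for its own coding; SAP 7.7 restores the direction without recording a correction, and SAP 7.8 and 2.3 are left inconsistent

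*Protocol*

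**What the plan says.** Write D1 and D2 for the mean changes in daytime ambulatory systolic pressure in arm 1 (amlodipine plus celecoxib) and arm 2 (amlodipine alone).

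- **Coding in the protocol.** Section 10.2.2 states: "Reductions will be, therefore, represented by positive numbers and increases by negative numbers". Section 10.2.3 defines each change as baseline minus Day 14. The synopsis (Statistical Methods for Primary Efficacy Analysis) says of the arm 1 symbol that it "is the reduction in SBP_{day} for subjects in arm 1".
- **Hypotheses in the protocol.** Section 10.2.3 and the synopsis both print H0: D1 - 0.5·D2 ≥ 0 and H1: D1 - 0.5·D2 < 0.
- **Intent in the protocol.** Section 10.2.3 says that the combination "is non-inferior to half of the effect achieved with the control treatment". Section 10.2.1 asks that the lower confidence limit for the "reduction in treatment arm 1 will be at least 50% of the mean reduction in treatment arm 2". Section 2.1 and the sample-size hypothesis in 10.9 and Appendix H.2 point the same way.
- **SAP.** Section 7.7 prints the same pair of inequalities but defines change as Day 14 minus baseline. Section 1.3.7 extends that recoding to all efficacy endpoints and says of it: "This change does not affect the absolute value of the results but gives a more intuitive interpretation of the direction of change". Section 1.3.5 describes the SAP's comparison as matching the protocol.

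**The concern.** When a fall is coded positive, keeping at least half the amlodipine effect means D1 - 0.5·D2 ≥ 0. The protocol places that state under the null and its opposite under the alternative, so rejecting the printed null would be evidence that the effect was lost. This is the primary hypothesis of a Phase 3 non-inferiority trial. Under protocol 10.2.5, a failed primary test also ends the efficacy testing.

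Protocol and SAP carry the same inequalities with opposite codings, so they state opposite hypotheses. A reader of SAP 1.3.5 and 1.3.7 would not learn this. Because the recoding was treated as presentational, its consequences were not followed into the secondary hypotheses or the wording of the success criterion.

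**Working it through.** **Direction, place by place**

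| Place | A fall is coded | Printed H1 | Matches the stated aim? |
|---|---|---|---|
| Protocol 10.2.3 and synopsis, daytime SBP | positive | < 0 | no |
| Protocol 10.2.5, 24-hour SBP and DBP | positive | > 0 | yes |
| SAP 7.7, daytime SBP | negative | < 0 | yes |
| SAP 7.8, 24-hour SBP and DBP | negative | > 0 | no |

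The recoding puts the primary hypothesis right and, with the other inequalities unchanged, puts the two secondary pressure hypotheses wrong. Creatinine clearance in SAP 7.8 is unaffected: an increase is the improvement, and > 0 is correct.

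**Inputs.** The prior-trial reductions are 10.6 mmHg (SD 9.2) for the combination and 8.8 mmHg (SD 8.1) for amlodipine (protocol 10.9 and Appendix H). There are 45 per arm (Appendix H.4.1, equal to 3/7 of 105). The one-sided level is 0.025 (SAP 1.3.11; protocol 10.9 printed 0.05, which the SAP calls an error). Normal approximation throughout.

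**The plan's own figure.** 10.6 - 0.5 × 8.8 = +6.2 mmHg, as stated. It is positive, so the planned result lies inside the printed H0.

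**Standard error of D1 - 0.5·D2.** √[(9.2² + 0.25 × 8.1²)/45] = √(101.04/45) = 1.50.

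**Results at the planning values**
- z = 6.2/1.50 = 4.14. The p-value for the printed H1 is 0.99998; for H1 > 0 it is 0.00002.
- The chance of rejecting is about 5 × 10⁻¹⁰ under the printed rule, and 98.5% with H1 > 0.
- The standard error implied by the sample-size formula is 8.7 × √(2/45) = 1.83. It gives z = 3.38, about 5 × 10⁻⁸ under the printed rule and 92.2% with H1 > 0.

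**Results if arm 1 has no reduction (D1 = 0, D2 = 8.8)**
- The contrast is -4.4 and z = -4.4/1.50 = -2.94.
- The printed rule rejects with probability Φ(2.94 - 1.96) ≈ 0.84. At one-sided 0.05 it is Φ(2.94 - 1.645) ≈ 0.90.
- With the formula's standard error it is Φ(4.4/1.83 - 1.96) ≈ 0.67 at 0.025.

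**SAP 2.3.** On the SAP's coding, success means that the contrast is below 0, so the upper one-sided 97.5% limit must be below 0. SAP 2.3 names the lower limit. Suppose arm 1 fell by only 2.4 mmHg against 8.8 in arm 2, which is 2.4/8.8 = 27% of the effect. The contrast is -2.4 + 4.4 = +2.0. The lower limit is 2.0 - 1.96 × 1.50 = -0.94, which passes as worded. The upper limit is 2.0 + 2.94 = +4.94, which fails as it should.

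**The case against.** The strongest reply is that nobody would run the test backwards. The protocol gives the right direction in words in its objective, its confidence-interval criterion, the lead sentence of 10.2.3 and the sample-size section. A reader who applied the 10.2.1 criterion would reach the intended conclusion. SAP 7.7 has the right direction, and its p-value is described as the probability at or above 0, which fits. The recoding is listed openly among the changes from the protocol, and the statement that absolute values are unaffected is literally true. All of this stands, and it limits the practical consequence for the primary analysis.

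It does not remove the gap in the record. The SAP does label another protocol slip as an error (the significance level, 1.3.11), yet it presents this recoding as a matter of interpretation. The reply also does not reach SAP 7.8 and 2.3, where the recoding was not carried through.

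Two stronger readings should be resisted. A reader might infer that the protocol as a whole defines failure as success; it does not, because only the printed H0/H1 pair conflicts with otherwise consistent text. A reader might also infer that the sign was changed with the results in view, since SAP v4.0 is labelled post-unblinding. SAP 1.5 also lists v3.0 as a final pre-unblinding version, and nothing in the documents shows which version introduced the recoding.

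**Conclusion.** The concern holds as an internal contradiction in the protocol's primary hypothesis, in both 10.2.3 and the synopsis. SAP 7.7 corrects it in effect, but the SAP does not document it as a correction. The operative primary test is not reversed.

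The 84% and the near-zero chance of success describe a literal application of the printed pair, which no document plans. They show that the sign matters and do not forecast what will happen. They rest on prior-trial means and SDs, 45 per arm and one-sided 0.025; other standard errors or levels move the 84% but not the direction. What remains live in the SAP is the reversed alternative for 24-hour systolic and diastolic pressure in 7.8 and the wrong confidence limit in 2.3.

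**What to change.** 1. In SAP 1.3.7, state that the protocol inequalities are reversed under the protocol's coding and should read H0: D1 - 0.5·D2 ≤ 0 and H1: D1 - 0.5·D2 > 0 for reductions coded positive. Add that the inequalities in SAP 7.7 hold only for endpoint minus baseline, and say in which SAP version the recoding was introduced. Align SAP 1.3.5 with this.
2. In SAP 7.8, change the 24-hour SBP and DBP alternatives to < 0. Leave creatinine clearance at > 0.
3. In SAP 2.3, require the upper one-sided 97.5% limit to be below 0.
4. Correct protocol 10.2.3 and the synopsis if they can still be amended. Amendments need ethics committee approval (protocol 13.3 and 15), so the SAP note is the realistic vehicle and is sufficient alone if amendment is no longer possible.

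The cost is a few sentences and signs in the SAP. The primary analysis need not be rerun. For the two secondary pressure tests, confirm that the programs use the < 0 tail.

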10.2.4 Secondary Efficacy Endpoints

Recall that subjects will be randomized 3:3:1 to one of three treatment arms:

1. OE Norvasc[®] tablet (10 mg amlodipine besylate) + OE Celebrex[®] capsule (200 mg celecoxib);

2. OE Norvasc[®] tablet (10 mg amlodipine besylate) + matched placebo for OE Celebrex[®] capsule;
3. Matched placebo for OE Norvasc[®] tablet + matched placebo for OE Celebrex[®] capsule.

A serial gatekeeping strategy will be used to evaluate the effect of amlodipine tablets (10 mg) and celecoxib capsules (200 mg) given together on secondary efficacy endpoints. If and only if the statistical significance is achieved for the primary efficacy endpoint, a secondary hierarchical analysis will be used to evaluate the endpoints listed below, and will only proceed to the next endpoint in the list if the alpha is met for the prior analyses.

1. Difference in mean change in body weight from baseline (Day 0) to Day 14 measurement (or if a LOCF is required, the Day 7 measurement) between treatment arms [amlodipine tablets (10 mg) and celecoxib capsules (200 mg) given together (arm 1), amlodipine tablets (10 mg) given alone (with matched celecoxib placebo) (arm 2), and placebo (arm 3)];
2. Difference in the mean reduction in SBP_{24h} from the baseline (Day -1 to Day 0) ABPM measurement to the Day 13 to Day 14 ABPM measurement (or if a LOCF is required, the Day 6 to Day 7 ABPM measurement) between subjects treated with amlodipine tablets (10 mg) and celecoxib capsules (200 mg) given together (arm 1) and amlodipine tablets (10 mg) given alone (with matched celecoxib placebo) (arm 2);
3. Difference in the mean reductions in DBP_{24h} from the baseline (Day -1 to Day 0) ABPM measurement to the Day 13 to Day 14 ABPM measurement (or if a LOCF is required, the Day 6 to Day 7 ABPM measurement) between subjects treated with amlodipine tablets (10 mg) and celecoxib capsules (200 mg) given together (arm 1) and amlodipine tablets (10 mg) given alone (with matched celecoxib placebo) (arm 2);
4. Difference in the mean change in creatinine clearance from baseline (Day 0) to the Day 14 measurement (or if a LOCF is required, the Day 7 measurement) between subjects treated with amlodipine tablets (10 mg) and celecoxib capsules (200 mg) given together (arm 1) and amlodipine tablets (10 mg) given alone (with matched celecoxib placebo) (arm 2).

10.2.5 Secondary Efficacy Endpoints Analysis

If the primary efficacy endpoint analysis fails to demonstrate statistical success, no further efficacy analyses will be performed. However, if it is successful, the following secondary hierarchical analysis to evaluate for the effect of amlodipine tablets (10 mg) and celecoxib capsules (200 mg) given together on secondary efficacy endpoints will be performed in the order listed. The analysis will only proceed to the next endpoint in the list if the alpha is met for the prior analyses.

1. Analysis of Variance (ANOVA) will be used to compare the changes in body weight among the three treatment arms. The omni-bus test will conclude if any differences exist with post-hoc comparisons identifying specific differences between treatment arms. Any statistically significant differences will be sufficient to pass this gate in the study-wide gate keeping strategy.

$$H_0: \Delta BW_1 = \Delta BW_2 = \Delta BW_3$$

$$H_1: \text{At least one difference, } \Delta BW_i - \Delta BW_j \neq 0$$

Where ΔBW_1 is the change, for subjects in arm 1, in body weight from the baseline measurement to the post-treatment measurement.

ΔBW_2 is the change, for subjects in arm 2, in body weight from the baseline measurement to the post-treatment measurement.

ΔBW_3 is the change, for subjects in arm 3, in body weight from the baseline measurement to the post-treatment measurement.

2. A two-sample t-test for superiority will be used to test the one-sided hypothesis that treatment with amlodipine tablets (10 mg) and celecoxib capsules (200 mg) given together (arm 1) lowers SBP_{24h} to a greater degree than amlodipine tablets (10 mg) given alone (with matched celecoxib placebo) (arm 2).

$$H_0: \Delta SBP_{24h,1} - \Delta SBP_{24h,2} = 0$$

$$H_1: \Delta SBP_{24h,1} - \Delta SBP_{24h,2} > 0$$

Where $\Delta SBP_{24h,1}$ is the change, for subjects in arm 1, in SBP_{24h} from the baseline ABPM measurement to the post-treatment ABPM measurement.

$\Delta SBP_{24h,2}$ is the change, for subjects in arm 2, in SBP_{24h} from the baseline ABPM measurement to the post-treatment ABPM measurement.

3. A two-sample t-test for superiority will be used to test the one-sided hypothesis that treatment with amlodipine tablets (10 mg) and celecoxib capsules (200 mg) given together (arm 1) lowers DBP_{24h} to a greater degree than amlodipine tablets (10 mg) given alone (with matched celecoxib placebo) (arm 2).

$$H_0: \Delta DBP_{24h,1} - \Delta DBP_{24h,2} = 0$$

$$H_1: \Delta DBP_{24h,1} - \Delta DBP_{24h,2} > 0$$

Where $\Delta DBP_{24h,1}$ is the change, for subjects in arm 1, in DBP_{24h} from the baseline ABPM measurement to the post-treatment ABPM measurement.

$\Delta DBP_{24h,2}$ is the change, for subjects in arm 2, in DBP_{24h} from the baseline ABPM measurement to the post-treatment ABPM measurement.

4. A two-sample t-test for superiority will be used to test the one-sided hypothesis that treatment with amlodipine tablets (10 mg) and celecoxib capsules (200 mg) given together (arm 1) improves creatinine clearance to a greater degree than amlodipine tablets (10 mg) given alone (with matched celecoxib placebo) (arm 2).

$$H_0: \Delta CC_1 - \Delta CC_2 = 0$$

$$H_1: \Delta CC_1 - \Delta CC_2 > 0$$

Where ΔCC_1 is the change, for subjects in arm 1, in creatinine clearance from the baseline creatinine clearance to the post-treatment creatinine clearance.

ΔCC_2 is the change, for subjects in arm 2, in creatinine clearance from the baseline creatinine clearance to the post-treatment creatinine clearance.

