The mean changes in average daytime (9:00 to 21:00) ambulatory systolic blood pressure (SBP_{day}), average daytime (9:00 to 21:00) diastolic blood pressure (DBP_{day}), average night-time (01:00 to 06:00) ambulatory systolic blood pressure (SBP_{night}), and average night-time (01:00 to 06:00) diastolic blood pressure (DBP_{night}) from baseline to end of therapy are listed below. Subjects in the amlodipine monotherapy arm had a mean reduction in SBP_{day} of 8.8 ± 8.1 mm Hg after 14 days of treatment, whereas subjects in the amlodipine + celecoxib arm had a mean reduction of 10.6 ± 9.2 mm Hg. The combination was shown to be statistically non-inferior to amlodipine alone ($p < 0.001$), and the primary efficacy endpoint of the study was successfully achieved. Further, the

change in SBP_{day} showed a synergistic effect with the combination over amlodipine monotherapy. The change in DBP_{day} showed a similar synergistic effect with the combination over amlodipine monotherapy and this synergy was even greater with respect to the SBP_{night} and DBP_{night} changes. Celecoxib monotherapy did tend to raise blood pressure (BP), not lower it, as expected, although statistical significance was not achieved.

**Changes in Blood Pressure from Baseline to End of Therapy
(Mean ± Standard Deviation mm Hg)**

	SBP_{day}	DBP_{day}	SBP_{night}	DBP_{night}
Placebo	-2.1 ± 8.2	-0.3 ± 5.4	-1.4 ± 9.2	0.0 ± 6.2
Celecoxib	-0.5 ± 8.8	-1.5 ± 5.1	-1.7 ± 12.3	0.3 ± 7.1
Amlodipine	-8.8 ± 8.1	-5.5 ± 5.1	-6.4 ± 11.4	-3.2 ± 7.8
Amlodipine + Celecoxib	-10.6 ± 9.2	-7.5 ± 6.4	-10.5 ± 10.6	-7.0 ± 8.6

Consistent with the known potential of celecoxib to alter renal physiology, the celecoxib monotherapy arm showed a trend towards worsened function as measured by the change in serum creatinine from baseline to end of therapy relative to the placebo arm. In contrast, the amlodipine monotherapy showed a trend towards improved renal function compared to placebo. Further, the combination of the two (amlodipine + celecoxib) showed a trend towards improved renal function that was greater than that noted for amlodipine alone.

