5.4 Hypertension

NSAIDs, including CELEBREX can lead to new onset of hypertension or worsening of preexisting hypertension, either of which may contribute to the increased incidence of CV events. Patients taking angiotensin converting enzyme (ACE) inhibitors, thiazide diuretics or loop diuretics may have impaired response to these therapies when taking NSAIDs [see *Drug Interactions* (7)].

The rates of hypertension from the CLASS trial in the CELEBREX, ibuprofen and diclofenac-treated patients were 2.4%, 4.2% and 2.5%, respectively [see *Clinical Studies* (14.6)].

Monitor blood pressure (BP) during the initiation of NSAID treatment and throughout the course of therapy.

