### **7.7. Primary Efficacy Analysis**

The primary efficacy analysis is to establish the non-inferiority of amlodipine tablets (10 mg) and celecoxib capsules (200 mg) given together (arm 1) with half the effect achieved with amlodipine tablets (10 mg) given alone (celecoxib placebo) (arm 2).

Statistics are based on the change in BP from the baseline ABPM measurement (Day -1 to Day 0) to the post-dose ABPM measurement (Day 13 to Day 14 or if a LOCF is required Day 6 to Day 7), as this represents the efficacy of the treatment. As indicated below, the change will be Day 13 to Day 14 minus Baseline and so a reduction will be a negative number. Sensitivity analysis will compare the results for the ITT population with those of the PP dataset and an MMRM analysis, if possible. A sensitivity analysis will also compare the results with the mITT population.

The hypothesis test being conducted is as follows:

$$H_0: \Delta SBP_{day,1} - 0.5(\Delta SBP_{day,2}) \geq 0 \text{ mmHg}$$

$$H_1: \Delta SBP_{day,1} - 0.5(\Delta SBP_{day,2}) < 0 \text{ mmHg}$$

Where  $\Delta SBP_{day,1}$  is the change, for subjects in arm 1, in the  $SBP_{day}$  from the baseline ABPM measurement ( $SBP_{day,1,base}$ ) to the final ABPM measurement ( $SBP_{day,1,14}$ ).

$$\Delta SBP_{day,1} = SBP_{day,1,14} - SBP_{day,1,base}.$$

$\Delta SBP_{day,2}$  is the change, for subjects in arm 2, in  $SBP_{day}$  from the baseline ABPM measurement ( $SBP_{day,2,0}$ ) to the final ABPM measurement ( $SBP_{day,2,14}$ ).

$$\Delta SBP_{day,2} = SBP_{day,2,14} - SBP_{day,2,base}.$$

This makes the actual test statistic:

$$\delta = \Delta SBP_{day,1} - 0.5(\Delta SBP_{day,2})$$

A one-sided 97.5% CI for  $\delta$  will be computed. In addition, a two-sided non-inferiority t-test comparing  $\delta$  to 0 will provide an appropriate p-value. This p-value will be computing the probability of observing a value  $\geq 0$  from a normal distribution for  $\delta$ .

Refer to the protocol Appendix H for further details regarding the efficacy analysis, and in particular the non-inferiority margin.

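### SBP24h, DBP24h and creatinine clearance get only one-sided superiority tests and no interval, so the formal inference cannot show a loss of amlodipine's 24-hour effect

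*Protocol*

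**What the plan says.** Protocol 10.2.5 item 2 reads: "A two-sample t-test for superiority will be used to test the one-sided hypothesis that treatment with amlodipine tablets (10 mg) and celecoxib capsules" given together lowers SBP24h more than amlodipine alone. The alternative is "H_1: \Delta SBP_{24h,1} - \Delta SBP_{24h,2} > 0". Item 3 does the same for DBP24h. Item 4 tests whether the combination "improves creatinine clearance to a greater degree than amlodipine tablets (10 mg) given alone", with alternative "H_1: \Delta CC_1 - \Delta CC_2 > 0". The tests are serial: "The analysis will only proceed to the next endpoint in the list if the alpha is met for the prior analyses". No alpha is stated for them.

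SAP 7.8 keeps these tests. SAP 1.3.18 adds that all four secondary endpoints are analysed whatever the outcome of the hierarchy. In the efficacy sections an interval is specified only for the primary contrast: "A one-sided 97.5% CI for" δ (SAP 7.7).

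On sign, Protocol 10.2.2 counts a fall in pressure as positive. SAP 1.3.7 and 7.8 redefine change as endpoint minus baseline, so a fall is now negative. SAP 7.8 items 2 and 3 still print the alternative as greater than zero.

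On direction, the protocol background says "Celecoxib monotherapy did tend to raise blood pressure (BP), not lower it, as expected". The celecoxib label in Appendix G says that NSAIDs, celecoxib included, "can lead to new onset of hypertension or worsening of preexisting hypertension". The prior trial also found amlodipine levels about one third lower with celecoxib. In that same trial, however, the combination lowered daytime systolic pressure more than amlodipine alone (10.6 v 8.8 mmHg). SAP 1.1 says the present study was designed to confirm that enhancement.

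**The concern.** The trial asks what celecoxib does to amlodipine's effect, and the documents' evidence on the answer runs both ways. A one-sided test for benefit can conclude only that the combination is better, or that this was not shown. A true loss and a true absence of difference lead to the same formal result.

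The primary analysis does not close the gap. It concerns daytime pressure and asks only whether half of amlodipine's effect is kept. Other outputs come near but do not supply the missing estimate:

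- Clinic SBP and DBP get an ANCOVA difference with a 95% CI (SAP 7.9), but Protocol 7.1 makes the ambulatory values the official ones for efficacy.
- SBP24h and DBP24h are summarised by arm in SAP 7.9, without a between-arm difference or interval.
- The exploratory arm 1 v arm 2 ambulatory tests (SAP 1.3.4, 7.10) are also one-sided for superiority.
- The peak and trough tests (SAP 7.10) are two-sided, but compare Day 6 with Day 13 rather than with baseline.
- The baseline-adjusted regression (SAP 1.3.3.3, 7.10) is for daytime pressure only, and no interval is specified for it.

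**Working it through.** **Inputs.** There are 45 subjects per main arm (Protocol Appendix H.4.1; 45 + 45 + 15 = 105). The SD is 8.7 mmHg, from Protocol 10.9: √((8.1² + 9.2²)/2) = 8.67. This is the SD of daytime change. The documents give none for 24-hour change, so its use here is an assumption. Arm 2's reduction is taken as 8.8 mmHg, as in the prior trial. The secondary alpha is assumed to be one-sided 0.025.

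**The plan's own figures.** No power or sample size is stated for these three endpoints. The primary formula in Protocol 10.9 with one-sided 0.025 gives 2 × ((1.960 + 0.842)/6.2)² × 8.7² = 30.9, so 31 per group. Appendix H.4.1 says 27, which SD 8.1 would give. This does not matter here, because 45 per group exceeds both.

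**Precision of the missing interval.**

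- SE = 8.7 × √(2/45) = 1.834 mmHg.
- Half-width = t(0.975, 88 df) × SE = 1.987 × 1.834 = 3.64 mmHg.
- Over other SDs: 2.9 at SD 7, 3.4 at 8.1, 3.9 at 9.2, 4.6 at 11. With 40 per arm and SD 8.7 it is 3.9.
- True loss that the interval would place wholly on the loss side with 80% probability: (1.960 + 0.842) × 1.834 = 5.1 mmHg (4.8 to 5.4 for SD 8.1 to 9.2).

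**One observed result, reported both ways.** Suppose arm 1 lowers SBP24h by 4 mmHg less than arm 2. With change as endpoint minus baseline, the arm 1 minus arm 2 difference is +4.

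- Test as worded (arm 1 lowers more): one-sided p = 0.984, so superiority is not shown.
- Two-sided 95% CI: 4 ± 3.64, or 0.4 to 7.6 mmHg, two-sided p = 0.03.
- Alternative as printed in SAP 7.8 (difference > 0): p = 1 − 0.984 = 0.016, which would count a loss as meeting the alternative.

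**How this interacts with the primary.** Assume the same loss in daytime pressure. The primary contrast, in terms of reductions, is (8.8 − loss) − 0.5 × 8.8 = 4.4 − loss, with SE = 8.7 × √(1.25/45) = 1.45. It passes with probability Φ((4.4 − loss)/1.45 − 1.960). The interval lies wholly on the loss side with probability Φ(loss/1.834 − 1.960). Both use the normal approximation.

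| True loss (mmHg) | Primary passes | Interval wholly on loss side |
|---|---|---|
| 2 | 38% | 19% |
| 3 | 16% | 37% |
| 4 | 5% | 59% |
| 6 | 0.1% | about 90% |

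At 4 mmHg the last column runs from 65% to 54% for SD 8.1 to 9.2.

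**The benefit side.** If arm 1 is truly better by 1.8 mmHg (10.6 − 8.8), the one-sided 0.025 test succeeds 16.4% of the time (25.4% at one-sided 0.05). A failed gate is therefore the likely outcome under a modest gain as well as under a loss, and on its own says little about which is true.

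**The case against.** **The documents expect benefit for the contrast tested.** This stands. SAP 1.1 reports that the enhancement reached significance for DBP24h in the prior trial. The fall in amlodipine levels was seen alongside larger pressure reductions. The celecoxib label's list of antihypertensives with impaired response does not name calcium channel blockers. Celecoxib alone was not uniformly worse than placebo either (daytime diastolic −1.5 v −0.3). A reader might infer from the label and the celecoxib-alone arm that the plan expects harm and tests the other way. The documents do not support that; they give grounds for both directions.

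**A loss would still be visible.** This largely stands. A reader might infer that a loss could be reported only as a failure to show superiority. In fact Protocol 10.2.4 defines the endpoints as differences between arms, and SAP 7.9 tabulates by-arm means and SDs from which an interval could be calculated. A one-sided p of 0.98 also looks different from one of 0.5. What is missing is a planned interval, not the data. SAP Appendix B, the list of tables, is not in the text available, so a table might carry one; SAP 7.8 does not ask for it.

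**The primary would catch a large loss.** This stands at 4 mmHg and above if daytime pressure shares the loss. It holds less well at 2 to 3 mmHg, where the primary passes 38% to 16% of the time. The interval would not settle losses of that size either, but it would show which values remain compatible with the data.

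**Renal function is already covered.** This mostly stands. The post-baseline components of Cockcroft-Gault clearance are weight and serum creatinine. Both have ANCOVA differences with 95% CIs, and for creatinine arm 1 v arm 2 is the primary comparison. Only the named endpoint lacks an interval.

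**One-sided superiority is a legitimate gate.** Agreed, and the gates are kept. A formal rule for declaring harm would add claims outside the hierarchy without multiplicity control, and an interval does not need one.

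**Conclusion.** The point holds as a reporting gap. For SBP24h, DBP24h and creatinine clearance the only specified arm 1 v arm 2 inference is a one-sided test for benefit. No planned analysis specifies a two-sided interval for the arm difference in ambulatory change from baseline. The gap matters most for 24-hour pressure and much less for renal function. It does not affect the primary test or the sample size.

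The missing interval would have a half-width of about 3.6 mmHg for SBP24h, or 2.9 to 4.6 over SD 7 to 11. This rests on 45 analysed per arm and on the borrowed daytime SD. The documents give no SD from which to do the same for DBP24h or creatinine clearance.

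Separately, the SAP 7.8 formulas for the two pressures contradict their own wording once change is endpoint minus baseline. A reader might infer that the SAP intends to test whether the combination lowers pressure less. The sentence above each formula says the opposite, so this is a sign left over from the protocol's convention. It still needs correcting, because followed literally it would credit a loss as a success. The creatinine clearance formula has the right sign.

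**What to change.** In SAP 7.8 items 2 to 4, report the arm 1 minus arm 2 mean difference with a two-sided 95% CI for SBP24h, DBP24h and creatinine clearance. Do so whatever the gate outcome, and describe it as an estimate outside the hierarchy.

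Keep the one-sided gates, but change the alternative for SBP24h and DBP24h to less than zero, so that it matches endpoint-minus-baseline change and the stated hypothesis that arm 1 lowers pressure more. State the alpha at which the gates are tested.

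SAP 1.5 describes version 4.0 as post-unblinding, so an interval added now should be labelled as added after unblinding.

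The cost is SAP wording and three table rows. No alpha is spent, no data are added, and the sample size is unchanged.
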